21 CFR 50.24

(a)(7) Additional protections of the rights and welfare of subjects will be provided, including at least:

(ii) Public disclosure to the communities in which the clinical investigation will be conducted and from which the subjects will be drawn, prior to initiation of the clinical investigation, of plans for the investigation and its risks and expected benefits;

(iii) Public disclosure of sufficient information following completion of the clinical investigation to apprise the community and researchers of the study, including the demographic characteristics of the research population, and its results;

Public disclosure will be done prior to enrollment and continue throughout the study period and after the study has completed. The study team will provide updates prior to and during the study period, and after the study has completed. The study results will be distributed locally and nationally through peer-reviewed journals, and presentations at national meetings.

Public disclosure is defined as the “dissemination of information about the research sufficient to allow a reasonable assumption that communities are aware of the plans for the investigation, its risks and expected benefits and the fact that the study will be conducted”. It also includes “dissemination of information after the investigation is completed so that communities and scientific researchers are aware of the study’s results”.

Appropriate public disclosure includes:

- Clear statement that informed consent will not be obtained for any subjects
- Information about the study medications use including a balanced description of the risks and benefits
- Synopsis of the research protocol and study design
- How potential study subjects will be identified
- Participating sites/institutions
- Description of the attempts to contact a LAR
- Suggestions for opting out of the study

Public Disclosure Planned

Using several different channels of communication for public disclosure increases the likelihood of reaching more of the intended audiences. It also can increase repetition of the message, improving the chance that intended audiences will be exposed to it often enough to absorb it. For these reasons, we will use a combination of channels.

Our plans for implementation include:

1. In-hospital Activities

We will post brochures and posters across Michigan Medicine Clinics, to include, the Emergency Department, Cardiology Clinics, employee areas, and any other are identified as relevant, before and during the trial. We will also utilize email messaging, to include M Headlines, M Research, The University Record, etc. These materials will provide a description of the study, local contact information, study website address, and opt-out information. All materials will be reviewed by IRB prior to use.

2. Community Activities

Obtain a booth/table at various local community events and hand out brochures and/or flyers describing study with contact information and talk with members of the community. We will target groups that appear to have interest in healthcare and/or cardiac disease, such as health fairs, American Heart Association (Ann Arbor), and organized walk/runs in the area as well as any other event where community members may gather in large numbers, such as libraries, sports facilities, concerts, fairs and festivals.

3. Electronic Resources

Electronic-based education is a passive approach to disseminating information that has benefits and challenges. There is no way to accurately measure whether how much of the community is reached by these methods. Access may be limited to those segments of the population with regular computer access. Despite these problems, electronic study education is inexpensive to develop and maintain and offers continuous and anonymous input from the public.

In collaboration with UMHS Department of Communication, we propose to advertise EROCA and EFIC in local appropriate websites and via paid social media advertising.

A copy of the press release or another IRB approved document will be submitted to neighborhood associations, requesting the information be shared. There are many on-line neighborhood associations who can reach hundreds of their neighbors through electronic means.

A copy of the press release or another IRB approved document will be submitted to City of Ann Arbor Communications Director requesting it be placed in their monthly newsletter that reaches all City of AA employees and approximately 500 community members on their mailing list.

2. BROADCAST AND PRINT MEDIA

Purchased advertising in broadcast and print media ensures dissemination of accurate materials to a wide audience. We plan to advertise in the paper and electronic versions of the local news papers.

In collaboration with UMHS Department of Communication, a news release will be written and IRB approved prior to distribution to any media.

Printed materials, including advertisements for publication in newspapers and magazines, brochures, and flyers will be reviewed and approved by the IRB . Advertisements will be purchased in both English language and foreign language newspapers as appropriate. All printed advertisements will provide a general description of the study, the national and/or local website address, as well as site contact information.

We also plan to contact local radio stations, who may be interested in covering the study and EFIC. Investigator appearances on local, radio, television, or call-in talk shows can bridge the line between public disclosure and community consultation.

Any local flyers or brochures distributed will reference EROCA study website as an additional resource for patients, families, and healthcare providers to get information as well as ask questions about EROCA.

Reporting Public Disclosure

All Public Disclosure activities will be summarized into a report and submitted to IRBMED for review.

Timeline for Community Consultation and Public Disclosure Activities

We anticipate beginning community consultation and public disclosure activities as soon as possible after IRB review and approval of our EFIC plan, with a goal of completion by January, 2017. The community consultation activities will occur over the course of about 5 months. Public disclosure will begin prior to study enrollment, will continue throughout study enrollment, and conclude with dissemination of study results after the study has concluded. We plan to initiate public disclosure activities at least 2-weeks prior to the start of the proposed trial. Public disclosure will continue beyond the end of study enrollment and through disclosure of study results, and anticipate a 1-3 year timeframe.

Analysis and Presentation of Results From Community Consultation and Public Disclosure

Reporting of community consultation results will be provided by the study team to the IRB. Summaries of the data will be reported to the FDA.

Data collected regarding CC and PD will include the following elements:

- Consultation methodology used
- Community type: geographic or condition-specific
- Participants involved: number and demographics
- Duration, content, format of information presented
- Free text log of comments, questions, and responses to open-ended questions
- Log of pre-determined closed-ended survey questions and responses

The study team will review survey responses and group meetings in summary form, and general themes will be summarized. The results of all local community consultation efforts will be summarized and submitted to IRBMED for review. If appointed and if present at the focus group discussions, an IRB liaison will provide an in-depth review of the discussions and additional feedback to the IRB as needed. Summaries of public disclosure will be reported to the IRB prior to approval, and then at least annually or upon request from the IRB.

A provision of the protocol has been made to allow participants who learn of the trial through community consultation or public disclosure or other means, and who would not want to participate if treated for a cardiac arrest, to opt-out of trial prior to such an event. Opt-out forms will be available on the Huron Valley Ambulance (HVA) and all community consultation interactions.

Contacting Legally Authorized Representatives (LAR) or family members

The federal regulations for contact of a Legally Authorized Representative (21 CFR 50.24) state:

(a)(7) Additional protections of the rights and welfare of the subjects will be provided, including, at least:

(v) If obtaining informed consent is not feasible and a legally authorized representative is not reasonably available, the investigator has committed, if

feasible, to attempting to contact within the therapeutic window the subject's family member who is not a legally authorized representative, and asking whether he or she objects to the subject's participation in the clinical investigation. The investigator will summarize efforts made to contact family members and make this information available to the IRB at the time of continuing review.

(b) The IRB is responsible for ensuring that procedures are in place to inform, at the earliest feasible opportunity, each subject, or if the subject remains incapacitated, a legally authorized representative of the subject, or if such a representative is not reasonably available, a family member, of the subject's inclusion in the clinical investigation, the details of the investigation and other information contained in the informed consent document. The IRB shall also ensure that there is a procedure to inform the subject, or if the subject remains incapacitated, a legally authorized representative of the subject, or if such a representative is not reasonably available, a family member, that he or she may discontinue the subject's participation at any time without penalty or loss of benefits to which the subject is otherwise entitled. If a legally authorized representative or family member is told about the clinical investigation and the subject's condition improves, the subject is also to be informed as soon as feasible. If a subject is entered into a clinical investigation with waived consent and the subject dies before a legally authorized representative or family member can be contacted, information about the clinical investigation is to be provided to the subject's legally authorized representative or family member, if feasible.

A procedure for prospective informed consent will be developed as is required by 21 CFR 50.24, in the unlikely event that a LAR can be identified within the presumed short therapeutic time window for the intervention and is able to provide a meaningful prospective surrogate consent for patient enrollment. However, it is highly unlikely consent will be obtained prospectively in this EROCA trial for the reasons summarized in the scientific protocol, to delay treatment of the patient in sudden cardiac arrest long enough to identify and contact either an LAR or other family members. In circumstances in which it is impossible to identify a LAR within the therapeutic time frame, EFIC will be applied.

Participants enrolled in EROCA under EFIC procedures and unable to consent, their LAR or family member(s) will be informed of the clinical investigation, including inclusion criteria at the earliest possible opportunity.

Participants enrolled in EROCA with EFIC, or their LAR/family member(s), will be informed of study enrollment in the clinical investigation at the earliest possible opportunity. Participants admitted to the hospital will be approached in person. A study team member will speak with the senior clinician to determine the stability of the participant and the appropriate time for speaking with the participant, or if not alert and capable of making informed decisions, a LAR or family member. The study team member will approach the participant(or LAR/family) to notify them about the participant's enrollment under EFIC, provide information about the study, including continued enrollment.

Participant's rights, the responsibilities of the investigators, and answer any questions about the study. At that time, the patient or the LAR will be asked to provide consent for continued participation in the study. A written informed consent document will be used to document the decision to either continue in the study or to not participate any further. A copy of this form will be provided to the participant and another copy will be placed in the research record.

Participants who do not wish to continue to participate will be excluded from all further aspects of the study except for the collection of data required by the FDA and permitted by the IRB to determine safety and efficacy. If informed consent is provided by a LAR or family member, we will approach the subject at the earliest possible opportunity to seek prospective, written informed consent for continuing participation in the study, should they become capable of doing so.

It is anticipated that the notification of participants of LAR/family member(s) will commonly take place in the hospital within 12-24 hours of their cardiac arrest. If the participant remains unable to participate in this process and family members or another legally authorized representative are not present, continued attempts will be made to contact an LAR. Attempts to notify the participant or an LAR will be repeated three times after the patient has been initially enrolled. All notification attempts will be recorded on the subject's case report form. Reports of these logs will be included in annual reports to the IRB.

If a participant is enrolled into EROCA and dies before a legally authorized representative or family member can be contacted, the investigators will send a letter with basic information about the clinical investigation, the subject's inclusion, and contact information to obtain more information or to answer questions if desired.

Due to the high mortality rate with sudden cardiac arrest, we expect many participants will die prior to coming to the hospital and a letter will be sent to their LAR and/or family member(s). If no contact members are identified in prehospital and hospital records, attempts will be made to locate one through an obituary search for a next of kin listing and if found, their contact information will be sought using on-line address sites.

For participants enrolled, who die prior to hospitalization, a letter will be sent to the participant's LAR/family member. The letter will include information about the study, their enrollment under EFIC, information collected, no further participation, contact information if they have questions.

Description of Refusal of Participation Procedures (Opt-Out)

Prior to and throughout the duration of the clinical trial, patients and their families will have various methods through which they can refuse participation in the trial. We will include this information at the community consultation meetings and on the brochures and posters for public disclosure. We will provide "File of Life" magnets, stickers, and cards at community events and have a link on our website to mail if requested.

APPENDIX B: UMHS ED ECPR GUIDELINES

Extracorporeal cardiopulmonary resuscitation (ECPR) is standard practice in the University of Michigan Hospital Emergency Department. ECPR utilizes a venous-arterial extracorporeal membrane oxygenation (VA-ECMO) circuit built from several components including. These 510K cleared devices may change based on the institutional practice of the hospital and are provided here as an example of the types of devices used.

QUADROX-iD Adult diffusion membrane Oxygenator
CentriMag Primary Console
CentriMag Back-up Console
CentriMag Motor
CardioHelp System

Inclusion/Exclusion criteria for ECPR

Inclusion Criteria:

- Age 18-70
- -Initial shockable (ventricular tachycardia or ventricular fibrillation) or witnessed pulseless electrical activity or witnessed asystole
- Anticipated interval from cardiac arrest onset (or 911 call) to establishing ECMO flow \leq 60 minutes
- Potentially reversible cause of cardiac arrest ¹

Exclusion Criteria:

[figure not shown]
- Sustained return of spontaneous circulation (ROSC)
- DNAR or DNI advanced directive
- Goals of care exclude ECPR (DNAR/DNI, advanced directive, or family discussion)
- Contraindication to anticoagulation ²
- Estimated BMI >40
- Advanced or life-limiting comorbidity ³
- Unable to independently perform ADLs at baseline
- Treating physician and/or ECMO consultant feels that ECPR is futile ⁴

(1) Potentially reversible causes of cardiac arrest include: ACS, refractory arrhythmia, myocarditis, massive PE, severe hypothermia, drug overdose

(2) Contraindications to anticoagulation include: Suspected or known intracranial hemorrhage, traumatic arrest, significant active bleeding

- (3) Advanced or life-limiting co-morbidities include: Stroke or CNS lesion with significant neurologic or cognitive impairment, liver cirrhosis including ESLD, ESRD, advanced COPD or other chronic lung disease, advanced or metastatic malignancy
- (4) Indications of futility are subject to the gestalt of the treating physician and/or ECMO surgeon, but may include: Septic shock multiorgan failure, hypoxemic arrest, metabolic acidosis with pH <7.0, Lactate >15, ETCO₂ <10 despite optimal ACLS, poor candidate for destination LVAD, artificial heart, or transplant

UMHS AES ECPR Protocol

- (1) Inclusion/Exclusion criteria per Appendix 1
- (2) Necessary resources will be determined case-by-case, with necessary available resources including: ECMO specialist or ECMO credentialed emergency department RN dedicated to sitting pump until transfer to CVC; CVC bed to be made available ASAP; ED and EC3 staffing/volume/capacity to care for ECPR patient; Availability of EC3 Intensivist by phone or in person

- (3) Initiation of ECPR includes femoral veno-arterial cannulation by an ECMO surgeon or an emergency physician credentialed for the procedure, as well as circuit and pump management by an ECMO specialist or ECMO-credentialed emergency department RN
- (4) Potential disposition destinations include: Cardiovascular center ICU; cardiac catheterization lab; and/or EC3, if EC3 intensivist and ECMO credentialed RN available

Standard data collected on cardiac arrest patients in UMHS AES

For internal review, quality improvement, and education, the following data elements are among those routinely obtained in patients with cardiac arrest and post-cardiac arrest care delivered in AES:

1. Time intervals, including time of arrest or 911 call, transport time, time of ED arrival, down-time, duration of CPR, time of return of circulation or initiation of ECPR
2. Drugs and shocks administered
3. Method(s) and device(s) used for CPR
4. Method(s) and device(s) used for airway management
5. End-Tidal CO2 measurements
6. Vital sign trends, with attention to diastolic blood pressure measurements when obtained invasively
7. Ventilator parameters, including settings and dynamic measurements
8. Blood gas results
9. Cerebral blood flow index via "C-Flow" device
10. Method(s) of therapeutic hypothermia, when utilized
11. Initial and subsequent cardiac rhythms
12. Return of circulation ECG interpretations
13. Bedside echocardiography images and interpretations
14. Cardiac catheterization results
15. ED, ICU, and hospital length of stay
16. EEG and neuro-prognostication results, including head CT, MRI, SSEP, NSE level, Neurology consultation documentation
17. Cerebral performance category upon discharge

Cardiac Arrest – General

This protocol should be followed for all adult cardiac arrests. Medical cardiac arrest patients undergoing attempted resuscitation should not be transported unless return of spontaneous circulation (ROSC) is achieved or transport is ordered by medical control or otherwise specified in protocol.

- ☑ If an arrest is of a known traumatic origin refer to the **Dead on Scene Protocol**.
- ☑ If it is unknown whether the arrest is traumatic or medical, continue with this protocol.
- ☑ Patients displaying a Do Not Resuscitate order or bracelet – follow **DNR Protocol**.
- ☑ When an ALS unit is present, follow this general cardiac arrest protocol in conjunction with the protocol that addresses the indentified rhythm.
- ☑ Once arrest is confirmed, emphasis should be on avoiding interruptions in CPR.
- ☑ CPR should be done in accordance with current guidelines established by the American Heart Association.

Pre-Medical Control MFR/EMT/SPECIALIST

1. Confirm Arrest
 - A. Assess for signs of normal breathing.
 - B. Check a carotid pulse for not more than 10seconds.
2. Initiate CPR or continue CPR if already in progress and apply and use AED as soon as available.
3. Ensure CPR quality
 - A. Compressions at least 2” in depth for adults.
 - B. Compression rate at least 100 per minute (An FDA approved mechanical CPR device operating at the manufacturer pre-set rate meets this rate requirement).
 - C. Avoid excessive ventilation (volume and rate).
4. Continue CPR with minimal interruptions, changing the rescuer doing compressions every 2 minutes, when possible.
5. Initiate ALS response if available.
6. Establish a patent airway, maintaining C-Spine precaution if indicated, using appropriate airway adjuncts and high flow oxygen. See **Emergency Airway Procedure**.

EMT

7. Establish a patent airway with a supraglottic airway. After insertion, provide continuous CPR without pauses for ventilation. Ventilations should be

EROCA – IDE Protocol Version 0.03

delivered at 8-10 breaths per minute or 1 breath every 5 to 6 seconds. See **Emergency Airway Procedure**.

8. Verify CPR quality frequently and anytime the rescuer providing compressions or ventilations changes.

9. If Return of Spontaneous Circulation (ROSC) has **not** been achieved after three, two minute cycles of CPR and ALS is not available or delayed, contact medical control, initiate transport.

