3 OBJECTIVES AND PURPOSE

Co-Primary: To determine what proportion of patients with refractory OHCA can be delivered to an ECPR-capable ED within 30 min of the 911 call or prehospital provider witnessed first cardiac arrest (qualifying OHCA event). This is to establish the feasibility of the early transport protocol.

Co-Primary: To determine what proportion of patients can have ECPR initiated within 30 minutes of ED arrival for patients with ongoing refractory OHCA. This is to establish the feasibility of the ED advanced resuscitation protocol in situations where prenotification of the team has occurred by qualified prehospital providers.

Safety: To estimate frequency of adverse events associated with study interventions. This early phase trial is not adequately sized to provide meaningful comparative estimates. The

population of OHCA survivors is at high risk for death and adverse experiences under routine clinical care.

Exploratory: Demonstrate the feasibility of field randomization of patients with refractory OHCA. This study is using a novel procedure to determine eligibility based on timing and location.

Exploratory: We will collect ECPR process measures including time to confirmed vascular access and confirmed ECPR cannulation. These measures are collected as part of routine clinical care on all patients undergoing ECPR for cardiac arrest at the qualified emergency department(s).

Exploratory: To provide preliminary estimates regarding neurological outcomes following this treatment. This study is not adequately sized to provide meaningful comparative data on neurological outcomes. This aim will provide insight into the proportion of patients with excellent outcomes, along with the proportion of patients with neurologically unsatisfactory outcomes.

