5.1.1 PATIENT LEVEL INCLUSION

- Present with out-of-hospital cardiac arrest, presumed non-traumatic etiology, requiring CPR
- Age presumed or known to be 18 through 70 years old (prior to 71st birthday)
- Predicted arrival time at ECPR-capable hospital within timeframe specified
- Initial shockable rhythm (ventricular tachycardia or ventricular fibrillation) or witnessed pulseless electrical activity or asystole
- Persistent cardiac arrest after initial cardiac rhythm analysis and shock (if shock is indicated)

Participants will be enrolled in the study if they meet initial inclusion criteria at the time of their cardiac arrest.

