5.2 PARTICIPANT EXCLUSION CRITERIA

Exclusion criteria include:

- Sustained return of spontaneous circulation (ROSC)
- DNAR or DNI advanced directive
- Preexisting evidence of opting out of study
- Prisoner
- Pregnant (obvious or known)
- ECPR capable ED is not at the destination hospital as determined by EMS
- LAR/Family member aware of study and refuses study participation at the scene

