6 STUDY INTERVENTION

This study is a comparison of two treatment strategies for refractory out-of-hospital cardiac arrest (OHCA): continued standard care in the field (control) versus expedited transport with ongoing mechanical CPR to a hospital capable of initiating extracorporeal cardiopulmonary resuscitation (ECPR) in the emergency department (experimental). ECPR is defined as percutaneous veno-arterial extracorporeal membrane oxygenation (ECMO) initiated during cardiac arrest. The duration of ECPR is typically 72 hours to allow the patient's heart function to recover prior to weaning. Many devices make up an ECMO circuit (cannulas, conduit, reservoir, pump, oxygenator, heat exchanger, monitors, sweep gas controller, bubble traps, blood filters, positive and negative pressure monitors and controls). The devices used for ECMO are FDA-approved for up to 6 hours for the indication of cardiopulmonary bypass. However, ECPR for the treatment of refractory cardiac arrest is not a FDA approved or cleared indication for ECMO devices, and thus is considered investigational in this study. Current American Heart Association Guidelines state that *"In settings where it can be rapidly implemented, ECPR may be considered for select cardiac arrest patients for whom the suspected etiology of the cardiac arrest is potentially reversible during a limited period of mechanical cardiorespiratory support (Class IIb, LOE C-LD)"*. ECPR is currently performed in the University of Michigan University Hospital ED for selected patients with refractory cardiac arrest as part of our standard practice. Examples of local guidelines for EMS and ED care are given as appendices B and C.

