7.3 STUDY SCHEDULE

7.3.1 SCREENING

Screening (Day 0, Field Baseline)

Screening will be done by prehospital providers in all out-of-hospital cardiac arrests in the engaged agencies area. All out-of-hospital cardiac arrests, meeting inclusion criteria will be considered for the study.

Pre Enrollment – Treatment Group Assignment / Randomization

At the time of dispatch of EMS, the dispatcher will enter the address of the arrest, age of the patient, and time of 911 call into a web form. The form will use an application to determine whether the patient is within the travel distance to arrive at the hospital within the pre-specified interval. They will immediately receive one of the following messages:

- 1) Not eligible, continue usual resuscitative care (patient may be out of geographic time area, may be over 71 years old)
- 2) Eligible, randomized to usual care
- 3) Eligible, randomized to early transport.

If the dispatcher is unable to access the assignment/randomization website, there will be a study team member, with access rights to the website available by telephone at all times.

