10.3 ANALYSIS DATASETS

The analytic datasets will use a modified per-protocol population. Patients who are assigned to early transport and do not have ROSC after initial rhythm analysis (and shock if indicated) and have the early transport initiated will be considered the primary analytic population for the ED arrival endpoint. Patients who are randomized to early transport and remain in cardiac arrest for at least 10 minutes after ED arrival and have the institutional standard care ECPR process initiated are considered the primary analytic population for the ECPR initiation endpoint. Exploratory clinical and safety endpoints will be collected on the entire population of refractory OHCA patients enrolled/randomized to either early transport or usual care.

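### Sections 10.3 and 10.4.2 define the ECPR co-primary denominator differently, so a patient in ongoing arrest who gets no ECPR because the service was unavailable is dropped under one and a failure under the other.

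*Combined protocol and SAP*

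**What the plan says.** **Denominator, section 10.3.** The datasets are labelled modified per-protocol. Early-transport patients must still be in arrest 10 minutes or more after reaching the ED. A further condition is then set, in that only those who "have the institutional standard care ECPR process initiated are considered the primary analytic population for the ECPR initiation endpoint".

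**Denominator, section 10.4.2.** The same endpoint is analysed in a modified intention-to-treat population in ongoing arrest in the qualified ED. Neither the 10-minute condition nor the process-initiated condition appears. Success is 80% or more started within 30 minutes, without a hypothesis test.

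**What ECPR depends on.** Appendix B, item 2 of the ECPR protocol: "Necessary resources will be determined case-by-case, with necessary available resources including". The list covers an ECMO specialist or credentialed nurse for the pump, a cardiovascular bed, ED and EC3 staffing and capacity, and an EC3 intensivist by phone or in person. Section 6 gives the appendix the status of an example: "Examples of local guidelines for EMS and ED care are given as appendices B and C".

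**Purpose.** Section 3 says of this co-primary: "This is to establish the feasibility of the ED advanced resuscitation protocol".

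**Data.** Section 7.3.2 abstracts the status of the ECPR procedure and its times. It lists no item for why ECPR was not started.

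**The concern.** Whether the team and equipment can be assembled when a patient arrives is part of whether the ED protocol is feasible. If patients enter the denominator only once the ECPR process has begun, the 80% figure describes speed when the service was available and says nothing about how often it was not. Removing these patients can only raise the proportion or leave it unchanged, since none of them can be a timely start. If patients enter because they are in arrest in the ED, the same figure covers both speed and availability. The plan states both definitions, so the analyst could choose between them after seeing which patients had no ECPR, and the choice can decide the verdict.

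**Working it through.** **The plan's own figure.** Section 10.5 gives 98% power for the arrival co-primary with n = 24, a null proportion of 38.7% and a true proportion of 19/24. The exact two-sided 0.05 test rejects at 4 or fewer or 15 or more arrivals (attained size 0.034), and its power is 0.983, so the figure reproduces. It is unaffected by this point. The plan gives no sample size or operating characteristic for the ECPR co-primary.

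**One patient, two scores.** Take an early-transport patient still in arrest 10 minutes after ED arrival, for whom no pump operator is free and the ECPR process is never begun.

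- Section 10.3: process not initiated, so not in the population.
- Section 10.4.2, read literally: in ongoing arrest in the qualified ED and no ECPR within 30 minutes, so a failure.

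**Effect on the verdict.** Let N be the number still in arrest in the ED, k those without resources and s the timely starts. The two results are s/(N − k) and s/N. All counts below are assumed.

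- N = 20, k = 3, s = 15, 2 late: 15/17 = 88.2% against 15/20 = 75.0%.
- N = 20, k = 4, s = 13: 13/16 = 81.3% against 13/20 = 65.0%.
- N = 10, k = 2, s = 7: 7/8 = 87.5% against 7/10 = 70.0%.
- N = 24, k = 1, s = 19: 19/23 = 82.6% against 19/24 = 79.2%. One patient is enough here.
- N = 20, k = 1: success needs 16 starts either way (16/19 = 84.2%, 16/20 = 80.0%), so one patient does not change the verdict.

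**Chance of declaring success.** Assume N = 20, a timely start in 85% when resources exist, and unavailability q.

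- Dropped: sum over m ~ Bin(20, 1 − q) of P(Bin(m, 0.85) ≥ 0.8m).
- Kept as failures: P(Bin(20, 0.85(1 − q)) ≥ 16).

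| q | Dropped (10.3) | Kept (10.4.2) |
|---|---|---|
| 1% | 80.4% | 80.0% |
| 2% | 78.4% | 76.7% |
| 5% | 74.9% | 66.2% |
| 10% | 73.9% | 47.7% |
| 20% | 75.1% | 18.3% |

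With a 90% timely rate instead, at q = 10%, 20% and 30%, the chances are 0.91, 0.91 and 0.90 if dropped and 0.67, 0.30 and 0.09 if kept. From 5% upward the first definition hardly responds to availability, while the second falls steeply.

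**The case against.** **Section 10.4.2 already keeps the patient.** Read literally it does, and it is the section that specifies the analysis. This stands, and it is why the point is a conflict between two sections rather than a settled exclusion. It does not remove the problem: 10.3 is the section that defines the datasets, and 10.4.2 could equally be read as shorthand for it.

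**Appendix B may be over-read.** It is an example, the bed is something to be found as soon as possible, the intensivist may be on the phone, and nothing says ECPR is withheld when an item is missing. ED ECPR is described as standard practice. This also stands. Appendix B shows how such a case can arise, not how often.

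**The size is assumed throughout.** Correct, and at 1–2% unavailability the two definitions nearly agree.

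**Stronger readings that a reader might infer.**

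- *That these patients are invisible.* They are not. ECPR status is abstracted, and section 10.4.10 tabulates individual data for the primary endpoints. Only a stated reason is missing.
- *That scoring their arrival as a success is wrong.* The first co-primary is there to show that early transport works, and a timely arrival is what it measures.
- *That dispatch should screen on availability.* It is true that "the dispatcher will enter the address of the arrest, age of the patient, and time of 911 call into a web form" and that the application tests only "whether the patient is within the travel distance to arrive at the hospital within the pre-specified interval". But dispatch is a pre-enrolment assignment, and section 5.2 later excludes when "ECPR capable ED is not at the destination hospital as determined by EMS". No real-time exchange of ED status is described, yet a dispatch screen would change who is transported early and would again take service failures out of the ECPR endpoint.

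**Conclusion.** The conflict between 10.3 and 10.4.2 is plain from the text and needs no assumption. Its consequence is that the same patient can be dropped or counted as a failure on a co-primary, and the 80% verdict can change with as few as one to three such patients, depending on how many are in arrest in the ED. How likely that is cannot be known from the documents. The figures rest on assumed values for the number in arrest, the timely rate and the unavailability rate, and range from negligible at 1–2% to a chance of success of 75% against 18% at 20%. The documents do not support saying that such patients will be lost from view, that the arrival endpoint is mis-scored, or that the 80% result is a formal gate to the larger trial.

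**What to change.** 1. Reconcile 10.3 and 10.4.2 with one denominator and one label. It should not depend on ECPR having been initiated, so that early-transport patients in ongoing arrest in the ED who are not started on ECPR because a resource was unavailable count as failures. State whether the 10-minute condition applies. State also how patients not started for the clinical reasons in Appendix B are counted, since the same conflict touches them.
2. Add one abstraction item in section 7.3.2: the reason ECPR was not started, for each early-transport patient in ongoing arrest in the ED.
3. Report the number not started for lack of a resource on its own line beside the 80% result.

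The cost is a short edit to two sections, one data item and one reporting line. The ECPR proportion may be less favourable. No change to eligibility, transport or treatment is needed.
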